### 7.3.2. Serious Adverse Event (SAE)

A serious adverse event is any undesirable adverse event or untoward medical occurrence (sign, symptom, illness, abnormal laboratory value, or other medical event) experienced by a patient during the course of the study that:

- Results in death;
- Is life-threatening;
- Requires inpatient hospitalization or prolongation of an existing hospitalization;
- Results in persistent or significant disability/incapacity;
- Requires intervention to prevent a permanent impairment of a bodily function or damage to a body structure.

Medical and scientific judgment should be exercised in determining whether an event is an important medical event. An important medical event may not be immediately life-threatening and/or result in death or hospitalization. However, if it is determined that the event may jeopardize the patient and may require intervention to prevent one of the other outcomes listed in the definition above, the important medical event should be reported as serious.

Examples of such events are intensive treatment in an emergency room for a bronchospasm or convulsions that do not result in hospitalization.

This definition of an SAE is not intended to include hospitalization specifically to treat a condition that existed prior to the patient's enrollment in the study (e.g., pre-existing cardiovascular disease that is treated during the study) or prearranged elective surgery performed during this study period.

## 7.4. Adverse Event Severity Determination

All Adverse Events must be classified by the investigator using mild, moderate, or severe to determine the level of severity of the AE as it relates to the evaluation of patient safety through the full course of the AE from initial reporting to the end of study for each patient who participates in this clinical study.

### ADVERSE EVENT SEVERITY

Mild	AE is noticeable to the patient but does not interfere with routine activity and does not require medical treatment.
Moderate	AE interferes with routine activity but responds to symptomatic therapy or rest. Usually requires medical treatment.
Severe	AE that results in loss of life or limb.

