## **7. ADVERSE EVENT (AE)**

### **7.1. Principal Investigator Responsibilities**

The Principal Investigator (PI) and/or staff participating in the study shall document all adverse events as defined in section 7.3 of this protocol. The severity of the AE and its relationship to the procedure / device will also be assessed by the PI. The PI will document on the CRF any relatedness descriptions that might apply to the AE (e.g. none, possible, probable, and definite). The sponsor will designate a monitor to review patient medical records at the study locations for indications of adverse events throughout the study to ensure appropriate documentation and reporting.

Reimbursement data collected in the study requires purchase of the Restrata™ material so that the investigator is able to submit for reimbursement from payers. The purchase price will be agreed upon within the Clinical Trial Agreement.

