# 8. DATA ANALYSIS

## 8.1. Demographics and Outcomes

Descriptive statistics will be used to compare amongst experimental groups, along with confidence intervals where appropriate to measure effect size. Rates of adverse events will be tabulated by type, severity and device / procedure relatedness. Furthermore, statistics on the wound measurements over time and at the 12 week endpoint will be used to inform future study hypotheses.

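### The section 7.4 severity scale leaves some adverse events without a grade, and section 8.1 does not explicitly tabulate serious events that patients survive

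*Combined protocol and SAP*

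**What the plan says.** Section 7.4 leaves no room for an ungraded event: "All Adverse Events must be classified by the investigator using mild, moderate, or severe". The severity table beneath it gives the three definitions, taken here from the top grade down:

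- The top grade, severe, is reserved for one kind of event: "AE that results in loss of life or limb".
- The middle grade, moderate, has two conditions and a remark on treatment: "AE interferes with routine activity but responds to symptomatic therapy or rest. Usually requires medical treatment".
- The lowest grade, mild, has three conditions, all of which must hold: "AE is noticeable to the patient but does not interfere with routine activity and does not require medical treatment".

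No section supplies a default or an other category.

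Section 7.3.2 defines an SAE by five criteria: death, threat to life, inpatient hospitalisation (new or prolonged), lasting or significant disability, and the need for intervention to prevent permanent damage. It adds important medical events, by judgement.

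Section 6.3 refers safety to section 8, and section 8.1 gives the safety analysis in one sentence: "Rates of adverse events will be tabulated by type, severity and device / procedure relatedness". Section 5.5 names type, severity and relatedness as the items to document. Neither section names seriousness.

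Section 7.1 tells the investigator to document AEs as section 7.3 defines them, and offers none as a relatedness category. Section 7.3 defines only device-related AEs and SAEs.

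**The concern.** Section 2.1 makes initial safety one of the study's purposes, alongside informing a randomised trial. The sentence in 8.1 is the only planned safety analysis, and severity is one of its three axes. If the grades do not cover every event, the investigator must force some events into a grade whose definition they fail, with no rule for choosing. The severity columns then mean less than they appear to.

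The upper end of the scale matters most. It goes from events that settle with symptomatic care or rest straight to death or amputation. A grave event that the patient survives with the limb intact cannot be shown as severe. Unless SAEs are also tabulated in their own right, it may sit among ordinary moderate events.

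The relatedness wording raises a smaller question of the same kind: whether non-serious, unrelated events are recorded at all, and so what the AE rates count.

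**Working it through.** No sample size, error rate or event rate enters here, and the plan states no figure to reproduce. The check is logical: write each definition as a rule and see which events satisfy none.

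**Inputs.** Five yes/no attributes, from the section 7.4 table: L, life or limb lost; N, noticed by the patient; I, limits routine activity; T, requires medical treatment; R, settles with symptomatic care or rest.

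**Rules as written.**
- Mild = N and not I and not T.
- Moderate = I and R. Treatment is only usual for this grade, so T does not decide it.
- Severe = L. Where L holds, the grade is taken as severe.

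**Count.** With L = no there are 2 × 2 × 2 × 2 = 16 profiles. Merging those that differ only in attributes that do not affect the grade gives five classes:

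| Class (no loss of life or limb) | Profiles | Grade now |
|---|---|---|
| I and R | 4 | Moderate |
| Not I, not T, N | 2 | Mild |
| A: I and not R | 4 | None |
| B: not I, T | 4 | None |
| C: not I, not T, not N | 2 | None |

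Graded: 4 + 2 = 6. Ungraded: 4 + 4 + 2 = 10. Total: 16. So three of five classes have no grade, and none has more than one.

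**Where serious events fall.** Of the five criteria in 7.3.2, only death fixes a grade. The other four lead to severe only if life or limb is lost. Assume that a survived serious event either limits activity or needs treatment, so that it is not mild. With the limb intact it is then moderate if it limits activity and settles with symptomatic care or rest; otherwise it has no grade. The criterion "Results in persistent or significant disability/incapacity" normally leads to class A: the event limits activity and, if persistent, has not settled.

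**Class B in practice.** A minor infection that is treated without limiting activity is an example. Infection is the one AE named among the tertiary outcomes in section 3.

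**Check of the rewording proposed under the fix.** Let M mean that the event responds to any medical treatment or rest. Symptomatic care is included, so R implies M.
- Severe = L, or (I and not M).
- Moderate = (I or T) and not severe.
- Mild = not I and not T and not severe.

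Over the 32 combinations of L, N, I, T and M, severe takes 16 (all with L) + 4 (no L, I, not M) = 20. Moderate takes 4 (I and M) + 4 (not I, T) = 8. Mild takes 4. The sum is 20 + 8 + 4 = 32, with no gap and no overlap. Events graded now keep their grade, because R implies M. Class A divides: events cleared by some other treatment become moderate, and those that respond to nothing become severe. B becomes moderate and C becomes mild.

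**The case against.** The best defence is that this is a single-arm descriptive series with AE incidence as a tertiary outcome, that investigators can use judgement at the edges of a scale, and that SAEs are defined, recognised and reported through IRB procedures (section 7.5). All of that is true, and it limits the point to grading and tabulation. It does not give class A a grade.

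Class B might be placed under moderate because that grade usually involves treatment. But that sentence describes moderate events, and the definition still requires interference. B is a gap on a literal reading; A is one on any reading.

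A reader might infer that SAEs will not be tabulated or captured at all. The documents do not support that. Type in 8.1 is undefined and could mean AE versus SAE; the list in 5.5 is not stated to be exclusive; section 7.3.2 tells investigators to report important medical events as serious; and the AE form is not shown. What stands is that the SAE tabulation is not explicit.

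A reader might also cite "sign, symptom, illness, abnormal laboratory value, or other medical event" as proof that unnoticed events will occur. That phrase belongs to the SAE definition, so it covers only values that also meet a seriousness criterion, and Appendix A lists no laboratory procedure during treatment. Nor does the provision "The sponsor will designate a monitor to review patient medical records at the study locations for indications of adverse events" show that such events exist. Class C stays a formal gap.

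A reader might divide the 30 patients by the 8 sites and argue that grading habits could not be told from real differences between sites. But 30 is a minimum in section 1 and 8 is a maximum in section 3, so the quotient is a floor rather than an expected average. Section 8.1 plans no comparison between sites.

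A fair objection to regrading is that a severe grade triggered by failure of symptomatic care alone would put an activity-limiting infection cured by antibiotics beside death. The wording below avoids this by counting response to any treatment. A lingering but minor event that limits activity would still be severe, which is one reason to show deaths and limb losses on their own lines.

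**Conclusion.** The point holds. Section 7.4 demands a grade for every AE and supplies definitions that cannot give one: three of five logical classes without loss of life or limb (10 of 16 profiles) are ungraded. Class A is the firm case, B follows on a literal reading, and C is formal. A life-threatening, hospitalised or disabling event survived with the limb intact can only be moderate or ungraded, and no table in 8.1 is explicitly planned to show it.

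The count describes the definitions; it does not estimate how many events will be affected, and the documents give no rate from which to do so. The conclusion assumes that the grade definitions are read as written and that type in 8.1 does not already mean serious versus non-serious. The harm is confined to the safety summary that is to inform the later trial; wound closure is untouched. The plan should be amended, but the study's main result does not depend on it.

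**What to change.** 1. **Tabulation (the essential part).** In 8.1, tabulate SAEs by 7.3.2 criterion and relatedness, separately from severity, with deaths and limb losses on their own lines. In 5.5, list seriousness among the AE items, with the criterion met. This is what makes survived serious events visible; regrading alone would leave many of them moderate.

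2. **Reporting grades in 7.4.** Make them exhaustive and mutually exclusive.
   - Mild: neither limits routine activity nor needs medical treatment, whether or not the patient notices it, and is not severe.
   - Moderate: limits routine activity or needs medical treatment, and is not severe.
   - Severe: life or limb is lost, or the event limits routine activity and does not respond to any medical treatment or rest over its full course, the period that 7.4 already uses.

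   These words govern classification for reporting only, not treatment.

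3. **Relatedness (secondary).** Reconcile 7.1 with 7.3 by stating that AEs are recorded whether or not related, with relatedness as an attribute.

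**Cost.** Three reworded grades, one clarifying sentence, one listed item (a new form field only if the form lacks it) and one table. Section 10.1 requires sponsor and IRB/IEC approval of the amendment, at up to 8 sites. AE rates may look slightly less favourable, because some events now without a grade become severe and more unrelated events may be recorded.

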## 7.5. Adverse Event Reporting

Investigators and /or study staff are required to report AEs per their Institutional Review Board Standard Operating Procedures (IRB-SOPs).

# 8. DATA ANALYSIS

## 8.1. Demographics and Outcomes

Descriptive statistics will be used to compare amongst experimental groups, along with confidence intervals where appropriate to measure effect size. Rates of adverse events will be tabulated by type, severity and device / procedure relatedness. Furthermore, statistics on the wound measurements over time and at the 12 week endpoint will be used to inform future study hypotheses.

# 9. DATA HANDLING AND RECORD KEEPING

## 9.1. Case Report Forms (CRFs)

Completed original CRFs are the sole property of Acera and should not be made available in any form to third parties, except for authorized representatives of appropriate regulatory authorities, without written permission from Acera.

It is the Principal Investigator's responsibility to ensure completion of CRFs by the clinical research team and to review and approve the data captured on all CRFs as accurate. All CRFs must be signed by the investigator. This signature serves to attest that the information contained on the CRFs is true. At all times, the investigator has final personal responsibility for the accuracy and authenticity of all data entered on CRFs. Subject source documents are the investigator's subject records maintained at the study site, and will be used to verify data documented on CRFs.

In some cases, a portion of the source documents for a given study/site may be the CRFs. For this study, the patient questionnaires' CRF pages will be considered source documents.

## **10. ETHICS**

### **10.1. Institutional Review Board (IRB)/Independent Ethics Committee (IEC)**

It is the responsibility of the investigator to obtain prospective approval of the conduct of the clinical study, the final protocol, protocol amendments, informed consent forms, and other relevant documents (e.g. advertisements), if applicable, from the IRB/IEC. Copies of the final IRB/IEC approvals must be forwarded to Acera prior to enrolling patients or starting any clinical study activities.

Protocol amendments require Acera and IRB/IEC approval before any patient in this clinical study is subjected to that change. When a change is necessary to eliminate apparent immediate hazards to the clinical study patients, emergency procedures can be used with caution to prevent exposing the patient to the hazard.

### **10.2. Ethical Conduct of the Clinical Study**

This clinical study will be conducted in accordance with the protocol, Good Clinical Practice (GCP) guidelines, and applicable local regulatory requirements and laws.

## **11. PATIENT INFORMATION AND INFORMED CONSENT**

The informed consent form must be agreed to by Acera and the IRB/IEC and must be in compliance with GCP guidelines, local regulatory requirements, and legal requirements.

The investigator must ensure that each study patient, or his/her acceptable representative, is fully informed about the nature and objectives of the clinical study and possible risks associated with participation in this study. The investigator will obtain written informed consent from each patient or their acceptable representative before any study-specific activity is performed. The informed consent form used in this study, and any changes made during the course of the study, must be

prospectively approved by both the IRB/IEC and Acera before use. The investigator will retain a copy of each patient's signed consent form.

## 12. SPONSOR DISCONTINUATION CRITERIA

Premature termination of this clinical study may occur because of a regulatory authority decision, change in opinion of the IRB/IEC, device safety concerns or at the discretion of Acera.

Acera reserves the right to discontinue the study prior to inclusion of the intended number of patients, but intends only to exercise this right for valid scientific or administrative reasons. After such a decision, the investigator must contact all participating patients within 30 days.

## 13. SUMMARY OF PROTOCOL REVISIONS

Revision Number	Date	Sections Revised	Summary of Changes
01	10/12/17	1, 3, 5.2 (subsections 4, 5, 6), 5.4, 13, and 14	Updated protocol sections for change in re-application rate of Restrata™ Wound Matrix from 4-week to weekly intervals.

## 14. APPENDICES

### Appendix A: Schedule of Events

Procedure	Run-In / Screening Period			Treatment Period Up to 14 Weeks												Closure Confirmation Visit
	First visit	End Week 1	End Week 2	Week 0	Week 1	Week 2	Week 3	Week 4	Week 5	Week 6	Week 7	Week 8	Week 9	Week 10	Week 11	Week 12
Informed consent	X															
Screening	X	X	X													
Demographics / medical history CRF	X															
Passed screening / enrollment CRF			X													
Device application CRF				X	X	X	X	X	X	X	X	X	X	X	X	
Wound assessment CRF and photo				X	X	X	X	X	X	X	X	X	X	X	X	X
Odor, itch, appearance CRF				X			X				X					X
Adverse event CRF				X	X	X	X	X	X	X	X	X	X	X	X	X
Reimbursement CRF				X	X	X	X	X	X	X	X	X	X	X	X	
Patient stipend					X	X	X	X	X	X	X	X	X	X	X	X

## **Appendix B: Supplies Provided by Acera**

- Clinical Report Forms (CRFs)
- Study binder
- Pregnancy tests
- Acetate tracing supplies
- Patient stipend cards
- Controlled ankle movement (CAM) walker boots
